On the outside of the prostate, within its outermost coverings, run the nerves thought to be responsible for producing erections. Preservation of these nerves has also been linked to more rapid reestablishment of urinary continence following surgical removal of the prostate. Robotic technology has been developed which allows the prostate to be removed through very small incisions. The surgeon's view is magnified in 3D, which facilitates the peeling off of the outer layers, containing the nerves (so called nerve sparing). With nerve sparing the nerves controlling erections are left intact whilst the prostate itself, along with the cancer within it, is removed. This increases the patient's chances of getting erections of sufficient quality for penetrative sex. Data from several case series, including our own, suggest that the higher the degree of nerve sparing performed, the more likely a patient is to be potent and continent of urine. In our series, bilateral nerve sparing results in 85% of men being able to get usable erections\*, whereas only 45% of men will have usable erections \* when only one side is spared.

Nerve sparing has largely been developed and the effects have been evaluated in the USA where prostate cancer is detected at an earlier stage because PSA screening is performed commonly. In the UK, where PSA screening is not commonly carried out, tumours resected at surgery are larger and more aggressive, often having spread

---

\* At 2 years following surgery using Viagra or an equivalent PDE5i.

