## 10.2 Multiparametric MRI prostate

All patients will have pre-biopsy mpMRI as per the local practice's diagnostic pathway. All radiologists will have at least 2 years of experience in prostate MRI reading. MRI diagnostic tumour detection performance is not formally assessed as all patients enrolling into NeuroSAFE PROOF already have tissue (biopsy) diagnosis of prostate adenocarcinoma and this is not the purpose of the trial. Radiologists are provided with clinical details including PSA, biopsy tumour results, biopsy method, medical history, and any other risk factors such as family history to aid their MRI interpretation. Local tumour staging (according to the PIRADS anatomic division of the prostate at the base, the mid gland and the apex) is graded according to a modified 5 level Likert scale based on the risk scoring system by the European Society of Urological Radiology (ESUR)(26), (1 = No signs of extra-prostatic extension (EPE), 2 = No convincing signs of EPE, 3 = EPE might be present, 4 = EPE is likely, 5 = EPE is highly likely).

Seminal vesicle invasion, lower sphincter invasion, and bladder neck invasion is reported as categorical ancillary reports. Subsequently, the radiologist using the mpMRI makes a NS recommendation for each side of the prostate for each participant regardless of treatment arm allocation. The radiological NS recommendation will be recorded:

- Nerve Sparing: Yes
- Nerve Sparing: No
- Digital rectal examination dependent.

Image-based mpMRI surgical NS planning is aimed to assist surgeons, but NS will still be performed in both control and intervention arm as per the operating surgeon's discretion.

During image based surgical NS planning, all mpMRI scans will be graded as to their quality according to the radiologist who reads the images. Scoring system will be a 1-5 Likert score. Description of criteria on scan required to give a quality score will be based on the following:

1. All three sequences are of insufficient quality to score any lesions.
2. Two out of the three sequences are not diagnostic; therefore, it is not possible to score any lesions.
3. It is possible to score a lesion (rule in) but it is not possible to exclude significant lesions (rule out).
4. One of the sequences is not of sufficient quality. Overall, it is possible to score the lesion (rule in) and rule out lesions in the background.

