Inclusion criteria	
 - Men opting to undergo RARP for organ confined prostate cancer (including radiological t3a). - Potent men (IIEF score of 22-25 on the first 5 questions of the IIEF-15 without any erectile function medical assistance) - Men who are continent of urine (no self-reported urinary incontinence) - Has given written informed consent - Ability to read English sufficiently to answer questionnaires and understand PIS

Exclusion criteria	
 - Unable to undergo RARP - Known overactive bladder - Any previous treatment for prostate cancer - Previous/current hormone treatment for prostate cancer - Nerve sparing deemed futile due to locally advanced disease by surgeon and radiologist
Number of sites	5
Study setting	Secondary care
Date of First Enrolment	10.10.18
Target Sample Size	Patient recruitment target in protocol: 404 patients Loss of follow-up: 10%
Primary Outcome	
 - IIEF-5 score at 12 months
Secondary Outcomes	
 - ICIQ at 3 months - ICIQ at 6 months - IIEF-6 at 12 months
Descriptive outcomes	
 - Time to erectile function recovery - Time to continence recovery - Positive surgical margins - Oncological outcomes at 12 months

1.2 *Objectives*

[figure not shown]

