3.4 Primary outcome definition

The primary outcome is the simplified International Index of Erectile Function (IIEF-5, Rosen 1999), at 12 months. The IIEF-5 is also known as the Sexual Health Inventory for Men (SHIM).

The questionnaire used in the study was based on the 15-item British Association of Urological Surgeons (BAUS) version of the IIEF (see Appendix 6.1).

The IIEF-5 score is obtained by summing the scores to the questions 2, 4, 5, 7 and 15, as described in Appendix 6.1.

The IIEF-5 score ranges from 1 to 25, with a higher score indicating better erectile function.

Handling of partially complete IIEF-5

For participants who answered at least half of the questions, we will replace any of the missing answers by the lowest score (0 for questions 2, 4, 5, and 7, and 1 for question 15), thus returning a conservative total score. For participants with 3 or more missing responses, we will consider the IIEF-5 score as missing.

This IIEF-5 definition will be also applied at baseline, visit 2 and visit 3.

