4.7 Primary outcome analysis

The primary estimand of interest will be the difference in mean IIEF-5 score at 12 months between participants allocated to the NeuroSAFE and those allocated to the standard treatment group among those who received the surgery.

The primary outcome (the IIEF-5 score at 12 month) will be analysed using a normal linear regression model. The model will include randomisation group, site (the stratification variable), age, and IIEF-5 at baseline. Continuous covariates (age and IIEF-5) will be included as a linear term, while site will be included as categorical. The estimated coefficient for the adjusted mean difference between randomisation groups will be presented alongside its 95% confidence interval and two-sided p-value

The primary analysis will include everyone in the mITT population with IIEF-5 available at 12 months.

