4.10.2 Interaction test

We will assess whether the effect of NeuroSAFE on IIEF-5 at 12 months and ICIQ at 3 months differs according to pre-operative bilateral nerve sparing recommendation (BNSR), as defined in 3.9.2.

This will be assessed by testing for an interaction between BNSR and treatment arm in the primary and secondary outcome models (linear regression adjusted by site, age and baseline IIEF-5 or ICIQ).

Interaction test p-values will be interpreted in consideration of the low power of the interaction test, the number of subgroups tested, and the biological plausibility of the interaction.

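### The primary and secondary models leave out the MRI nerve-sparing recommendation, a baseline variable the trial already holds; adding it before unblinding would probably buy a little precision

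*SAP*

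**What the plan says.** SAP 4.7 states that 12-month IIEF-5 "will be analysed using a normal linear regression model" and lists the terms: "The model will include randomisation group, site (the stratification variable), age, and IIEF-5 at baseline". SAP 4.8 uses analogous models for ICIQ at 3 and 6 months and IIEF-6 at 12 months, each with its own baseline score.

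The MRI recommendation is available in both arms. Protocol 10.2 says that "the radiologist using the mpMRI makes a NS recommendation for each side of the prostate for each participant regardless of treatment arm allocation". SAP 3.8 turns it into a yes/no variable, BNSR, calls it baseline, and treats a man with either side unrecorded as missing. BNSR then appears in two places only: SAP 4.10.2, by "testing for an interaction between BNSR and treatment arm in the primary and secondary outcome models", and SAP 4.10.3, which repeats the comparison in men without BNSR, expected to be about two thirds of the trial.

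Two further statements bear on the point. The eligibility criterion in SAP 1.1 requires an "IIEF score of 22-25 on the first 5 questions of the IIEF-15", whereas SAP 3.4 defines the outcome and its baseline value differently: "The IIEF-5 score is obtained by summing the scores to the questions 2, 4, 5, 7 and 15". And Protocol 3.1 reports from the investigators' own series that "bilateral nerve sparing results in 85% of men being able to get usable erections", against 45% when one side is spared; a footnote places this at 2 years with a PDE5 inhibitor.

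**The concern.** In a randomised comparison of a continuous outcome, adjusting for a prognostic baseline variable narrows the confidence interval without recruiting anyone else. Of the patient-level covariates in the primary model, baseline IIEF-5 has a limited range because only potent men are eligible. BNSR is a plausible addition. In the control arm the MRI planning sheet helps decide how much nerve is spared (Protocol 10.1.1), and the investigators' series links sparing to erections. In the NeuroSAFE arm, a qualifying positive frozen section leads to removal of the whole bundle (Protocol 10.1.2). SAP 4.10.1 regards a bilateral recommendation as almost always correct, so these resections should fall mainly on men without BNSR.

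Randomisation is stratified by site only (SAP 1.5), so chance imbalance in BNSR between the arms is not controlled by design either. At stake is a modest amount of precision on the primary estimate, not its validity.

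**Working it through.** **Inputs from the documents.** 364 evaluable men, 1:1 allocation, two-sided 5%, 80% power, 42% against 28% (SAP 1.4); about two thirds of men without BNSR (SAP 4.10.3), so the variance of the BNSR indicator is (1/3)(2/3) = 2/9.

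**Inputs assumed.** The documents give neither the SD of 12-month IIEF-5 nor the gap *D* in mean score between men with and without BNSR. I take SD = 7 and *D* = 1 to 4 points, where *D* is the gap averaged over the two arms.

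**The plan's own figure.** Pooled two-proportion formula without continuity correction: n per arm = [1.960 × √(2 × 0.35 × 0.65) + 0.842 × √(0.28 × 0.72 + 0.42 × 0.58)]² / 0.14² = 181.02, rounded up to 182. The total is 364, as stated. 364/0.9 = 404.4, against 404 stated. This sizing is for a binary endpoint, so the equivalent numbers and power below are relative shifts from 364 men and a nominal 80%. They are not the true power of the continuous analysis.

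**How restricted is the baseline score?** Eligibility limits the sum of questions 1–5 to 22–25. Questions 1 and 3 contribute at most 10, so questions 2 + 4 + 5 total at least 12. Question 7 can be 0 and question 15 can be 1. The baseline IIEF-5 can therefore run from 12 + 0 + 1 = 13 up to 25. Even if it were confined to 22–25, its SD could reach 1.5; with an assumed slope of 1 it would explain (1.5/7)² = 4.6% of the variance.

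**Gain from adding BNSR.** R² = (2/9)*D*²/SD²; SE ratio = √(1 − R²); equivalent N = 364/(1 − R²); power = Φ[(1.960 + 0.842)/√(1 − R²) − 1.960].

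| *D* (arm-averaged) | R² | SE ratio | SE reduction | Extra men, equivalent | Power from 80% |
|---|---|---|---|---|---|
| 1 | 0.5% | 0.998 | 0.2% | 2 | 80.2% |
| 2 | 1.8% | 0.991 | 0.9% | 7 | 80.7% |
| 3 | 4.1% | 0.979 | 2.1% | 15 | 81.6% |
| 4 | 7.3% | 0.963 | 3.7% | 28 | 82.9% |

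Here 7 is the total SD. If 7 is instead the SD within BNSR groups, R² = (2/9)*D*²/(SD² + (2/9)*D*²) and the 4-point row becomes 6.8% and 3.4%. Over within-group SDs of 6 to 8, gaps of 2 to 4 points give SE reductions of 0.7% to 4.6%.

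**Unequal gaps by arm.** SAP 4.10.1 expects NeuroSAFE to help men without BNSR more, so the gap should be smaller in the NeuroSAFE arm. Simulation at n = 364, within-group SD 7 and BNSR in one third, comparing models with and without a BNSR main effect:

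| Gap, control / NeuroSAFE | SE ratio |
|---|---|
| 0 / 0 | 1.001 |
| 2 / 0 | 0.999 |
| 4 / 0 | 0.993 |
| 4 / 2 | 0.982 |
| 4 / 4 | 0.967 |

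**Chance imbalance.** The between-arm difference in BNSR share has standard error √[(2/9)(4/364)] = 4.9 percentage points, so differences up to about 10 points are within chance. At *D* = 4, that moves the unadjusted estimate by about 0.4 points. This is the same gain seen from another side and does not add to it.

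**The case against.** The strongest reply is that nothing is wrong with the model. It contains the stratification factor, age and the baseline value of the outcome, it is pre-specified, and BNSR is already used where it matters scientifically. That stands.

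A reader might infer that eligibility pins the covariate to 22–25, leaving it nearly useless. The documents do not support this. The eligibility score and the covariate share only three items, and the covariate can range from 13 to 25. It is range-limited, and how much it explains is unknown.

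A reader might also take the 85% and 45% figures as proof that BNSR is strongly prognostic. They describe sparing actually performed, usable erections, 2 years and a PDE5 inhibitor. If the whole contrast carried over to BNSR in both arms, R² on that binary scale would be (2/9)(0.40²)/(0.583 × 0.417) = 14.6%; half of it gives 4.4% and a quarter 1.3%. The full figure is an upper bound because the link is diluted. Every NeuroSAFE patient starts with bilateral sparing where technically possible, controls are also guided by biopsy and rectal examination, and sides marked as dependent on rectal examination count as non-BNSR.

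Two further cautions stand. The R² above is marginal, so any overlap between BNSR and site, age or baseline IIEF-5 reduces the gain. Timing is also unsettled: both assessment schedules (Protocol 7.4, SAP 3.1) list MRI-guided surgical planning in the treatment column, after randomisation, although SAP 3.8 calls the recommendation baseline. The surgeon knows the allocation (Protocol 9.2), and the documents do not say whether the radiologist does.

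**Conclusion.** The point holds as an efficiency suggestion of low severity. BNSR is collected in both arms, defined in the SAP and absent from the primary and secondary models. If the recommendation was made before randomisation or blind to allocation, adding it cannot bias the randomised comparison.

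A realistic reduction in the standard error is roughly 1% to 3%. It rests on an assumed SD near 7, one third of men with BNSR, and an inferred prognostic effect. It falls below 1% if the gap exists only in controls and is 4 points or less, and to nothing if BNSR does not predict the outcome. A larger claim, such as a 6% reduction worth about 47 men, would need an arm-averaged gap of 5 points: 5 in both arms, or 10 in controls with none under NeuroSAFE. The documents give no basis for that. Nor do they allow a figure for the ICIQ models, for which no SD or gap is stated, although Protocol 3.1 and 4.2 link the nerves to continence.

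**What to change.** Before unblinding, add BNSR as a main-effect covariate to the models in SAP 4.7 and 4.8. State there how missing values are handled: either add BNSR to the covariates covered by the mean or mode imputation rule in SAP 4.1.2, or use a separate missing category. The primary model is then nested in the interaction model of SAP 4.10.2.

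First confirm from the recorded dates that the recommendation was made before randomisation, or document that it was made blind to allocation. If neither can be shown, use clinical T stage or Cambridge prognostic group, both listed as baseline in SAP 3.9.2. Their link to erectile function is not documented either, so the gain from the fallback is unknown.

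The cost with BNSR is one degree of freedom, or two with a missing category, plus the date check. The choice should be fixed in the SAP and not made after the arms have been compared. SAP 4.11.1 does not cover it, since it allows extra baseline adjustment only for predictors of missing data.

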4.8 Secondary outcomes analysis

The secondary outcomes (ICIQ at 3 months, ICIQ at 6 months, IIEF-6 at 12 months) will be analysed using linear regression analogous to the primary outcome analysis. The models will include randomisation group and site, age and corresponding outcome (ICIQ or IIEF-6) score at baseline. It will be based on the mITT patients with relevant outcome data available.

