## 7.2.2 Secondary Endpoints

### 7.2.2.1. Urinary Continence

Comparison of the proportion of men who are continent at 3 months, measured using the ICIQ PROM, where continence is defined as a score of 5 or less, between the NeuroSAFE RARP arm and the standard RARP arm.

- Sensitivity analyses: Analysis of incontinence at 6 months ICIQ score of 5 or less
- Additional subgroup analysis: restricted to men who did not receive a pre-operation radiologist recommendation for bilateral nerve sparing.
- Additional subgroup analysis: patients who did not receive adjuvant treatment (adjuvant therapy defined as any additional treatment without a  $PSA > 0.2 \text{ ng/ml}$ )
- Descriptive analysis of ICIQ scores at 3-, 6-, 12- and 24-months post-surgery

---

 Analysis after 12 months dependent on future funding

 Analysis after 12 months dependent on future funding

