## 12 STATISTICS

### 12.1 Sample size

As of protocol version 5.0, the NeuroSAFE sample size justification has been updated based on the analysis of 50 patients included in the NeuroSAFE PROOF Feasibility Trial, which was relevant to the original version of this protocol. 25 men were randomly allocated to NeuroSAFE RARP and 25 allocated to standard RARP. They were then followed up to 12-months following treatment. Outcomes related to these men will not be included in main trial analysis.

Based on analysis of the feasibility trial outcomes, the primary outcome was defined as a comparison of erectile function recovery at 12-months between men who underwent NeuroSAFE RARP (intervention) vs. standard RARP (control) with recovery defined as an IIEF-5 score of 21 or above.

The previous recruitment target according to protocol version 4.0 (August 2019) was for 404 men (364 evaluable). This sample size was calculated without the benefit of mature functional (i.e. PROMs/IIEF-15) results related to erectile function recovery.

A new sample size using the newly informed outcome data from the feasibility trial was prepared for protocol 5.0. The sample size is based on a 14% higher proportion of men with IIEF-5 score of 21 and above in the NeuroSAFE RARP (intervention) arm, compared to the control baseline proportion. At 90% power, an alpha of 0.05 and a loss to follow up of 10%, 416 patients (374 evaluable) would be the anticipated recruitment target. This sample size calculation is therefore deemed to be compatible with the sample size calculation submitted and used within protocol version 4.0 (August 2019). Furthermore, the iDMC reviewed the sample size assumptions on 16th Feb 2021 and were unblinded to results from the first 150 men recruited to the main trial. They advised the trial continue recruitment to the original number of 404 men (364 evaluable men). The iDMC will continue to review the recruitment target during the trial.

The secondary outcome #1, the proportion of men regaining continence at 3 months as defined by ICIQ score of 5 or less, is powered at 89% for a 15% increase in the NeuroSAFE RARP (intervention) arm compared to the standard RARP (control) arm at 3 months.

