Results of the feasibility trial used for sample size calculation have been redacted from this protocol document, as these are anticipated to be similar to interim results for the full powered ongoing trial, due to the internal design of feasibility trial which shared the same methods and centres as the main trial. The intention of restricted access to these preliminary results, is that these results should not influence recruitment to the main trial, because the feasibility trial was not powered to provide estimates of the primary or secondary outcomes. Full unblinded results

needed for sample size calculation are available in confidence for research ethics review and iDMC.

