### 12.2.4 Statistical methods

Primary outcome: Comparison of the unpaired proportions of men who recover erectile function at 12 months allocated to the NeuroSAFE intervention versus the control arm, based on an IIEF-5 score of 21 or more. Statistical significance will be established using 95% confidence intervals calculated using the Wilson method. P-values will be reported. Further planned subgroup and sensitivity analyses will be conducted as detailed in section 7.2.1

The secondary outcome #1 will use similar methods to the primary outcome.

There will be no adjustment of p-values for secondary outcomes for multiple testing. STATA statistical software will be used.

Due to interruption the trial due to COVID pandemic, collection of outcomes at particular time points has been affected, with 3- and 6-month time points being less regimented than anticipated. Prior to data lock, the statistical methods will be

reviewed. It is possible that analysis could use survival analysis of time to event analysis up to 12 months for both analyses, if that would make better use of data from multiple time points.

Statistical methods will be reviewed on analysis of a sample of 20% of all data prior to data lock, after data collection and cleaning.

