3.2 Outcomes list

Primary outcome:

- IIEF-5 (the simplified International Index of Erectile Function) at 12 months.

Secondary outcomes:

- ICIQ (International Consultation on Incontinence Questionnaire) at 3 months *
- ICIQ at 6 months
- IIEF-6 at 12 months

* Main secondary outcome of interest is ICIQ at 3 months.

Descriptive outcomes:

- Erectile function recovery at 3, 6 and 12 months (binary and categorical)
- Time to erectile function recovery
- Continence recovery at 3, 6 and 12 months (binary)
- Time to urinary continence
- Oncological outcome at 12 months
- Positive Surgical Margins

Additional descriptive data will also include baseline characteristics, surgery and histopathology information, and serious adverse events, as described below.

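### The SAP tests mean ICIQ but plans no between-arm estimate for the protocol's powered secondary endpoint, the proportion continent (ICIQ 5 or less) at 3 months

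*SAP*

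**What the plan says.** **Protocol.** Section 7.2.2.1 defines the endpoint as "Comparison of the proportion of men who are continent at 3 months, measured using the ICIQ PROM", with continence meaning a score of 5 or less. It adds the same analysis at 6 months as a sensitivity analysis and a subgroup restricted to men without a radiologist recommendation for bilateral nerve sparing. Section 12.1 says this outcome "is powered at 89% for a 15% increase in the NeuroSAFE RARP (intervention) arm compared to the standard RARP (control) arm" at 3 months. Section 12.2.4 says "The secondary outcome #1 will use similar methods to the primary outcome"; for the primary outcome that means unpaired proportions, 95% confidence intervals by the Wilson method, and p-values.

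**SAP.** Section 3.2 names ICIQ at 3 months, as a score, the main secondary outcome. Section 4.8 says the secondary outcomes "will be analysed using linear regression analogous to the primary outcome analysis", adjusted for site, age and the baseline score. The binary form, "Continence recovery at 3, 6 and 12 months (binary"), is listed in section 3.2 among the descriptive outcomes. Section 4.6 gives categorical variables frequencies and percentages by arm. Section 4.9.3 plots time to ICIQ 5 or less as a Kaplan-Meier curve by arm, with no test. Section 4.1.3 counts one primary and three secondary tested outcomes, all of them scores. In the non-BNSR subgroup, section 4.10.3 models the ICIQ score at 3 months and leaves descriptive outcomes to optional reporting without testing.

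**The concern.** The two documents ask different questions of the same questionnaire. The protocol asks whether more men reach continence by 3 months. The SAP asks whether the average ICIQ score differs. On a 0 to 21 scale with a threshold at 5, the answers can diverge. A mean difference can come from men with severe leakage who improve but stay incontinent. A real gain in men crossing the threshold can also be a small change in the mean.

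At stake is the protocol's lead secondary comparison. As the SAP stands, the trial would report two percentages and a curve for it, with no pre-specified measure of uncertainty around their difference.

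**Working it through.** **1. The two plans side by side**

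| | Protocol 7.2.2.1, 12.1, 12.2.4 | SAP 3.2, 4.6, 4.8, 4.9.3 |
|---|---|---|
| Tested quantity at 3 months | Proportion with ICIQ 5 or less | Mean ICIQ score |
| Method | Unpaired proportions, Wilson CI, p-value | Linear regression (site, age, baseline ICIQ) |
| Proportion continent | Compared between arms | Counts by arm and an untested Kaplan-Meier curve |
| Stated power | 89% for +15 points | None for ICIQ in either form |

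**2. Check of the formula on the SAP's own sample size**

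Inputs from SAP 1.4: 28% v 42%, 80% power, two-sided 5%.

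n per arm = [1.960√(2p̄q̄) + 0.8416√(p₁q₁ + p₂q₂)]² / (p₂ − p₁)²

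With p̄ = 0.35 this gives 181.02, rounded up to 182, or 364 in total. That is the SAP figure.

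**3. Is 89% attainable for the proportion?**

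The control continence rate is not public; protocol 12.1 says "Results of the feasibility trial used for sample size calculation have been redacted from this protocol document". It is therefore an assumption here and is varied. I also assume two-sided 5% and 182 evaluable men per arm at 3 months.

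Power = Φ{[0.15 − 1.960√(2p̄q̄/n)] / √[(p₁q₁ + p₂q₂)/n]}

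Worked case, control 21% v 36%: √(2p̄q̄/n) = 0.04732 and √[(p₁q₁ + p₂q₂)/n] = 0.04666. Power = Φ[(0.15 − 0.0927)/0.04666] = Φ(1.227) = 89.0%.

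| Assumed control rate | Power for +15 points, 182 per arm |
|---|---|
| 10% | 96.7% |
| 20% | 89.7% |
| 21% | 89.0% |
| 30% | 84.3% |
| 45% | 82.0% |
| 60% | 86.6% |
| 64% | 89.0% |
| 70% | 93.2% |
| 75% | 96.7% |

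With 187 per arm (the protocol's 374 evaluable men), 89% is reached near 22% or 63%. So the 89% is consistent with a two-proportion test, but it cannot be confirmed without the redacted rate.

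**4. Does 89% carry over to the mean?**

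This cannot be computed, because neither document gives an ICIQ standard deviation or a target mean difference. With 182 per arm, 89% power corresponds to a standardised difference of (1.960 + 1.227) × √(2/182) = 0.33 SD. Two assumed patterns show that the direction is open:

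- *Broad shift.* Suppose continence is a cut-point on a normal score and the whole distribution moves. From 45% to 60% the shift is 0.38 SD: power 95% for the mean, 82% for the proportion. From 21% to 36%, or 64% to 79%, it is 0.45 SD: 99% against 89%.
- *Narrow shift.* Suppose 15% of men each improve by 3 points across the threshold and nobody else changes, taking 45% to 60%. The mean moves 0.15 × 3 = 0.45 points. With an assumed SD of 6.43, the standard error is 6.43 × √(2/182) = 0.674 and power is about 10%, against 82% for the proportion.

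**5. Precision of the missing estimate**

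Half-width = 1.96 × √[(p₁q₁ + p₂q₂)/182], for a 15-point difference:

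- Control 15% or 70%: 1.96 × √(0.3375/182) = 8.4 points.
- Control 42.5% (the widest case): 1.96 × √(0.48875/182) = 10.2 points.

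SAP 4.10.3 expects about two thirds of participants to be non-BNSR, or about 121 per arm if split evenly. Multiplying by √(182/121) = 1.23 gives roughly 10 to 12.5 points in that subgroup.

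**The case against.** The best defence is that the SAP made a legitimate choice not to dichotomise a score. The protocol deferred detail to a SAP and said the methods would be reviewed before data lock. The two statisticians responsible for the SAP are recorded as blinded to allocation, and the SAP is to be public before unblinding. The hypothesis and objective speak of continence recovery without naming a proportion; only the endpoint text does. Under a broad shift in scores the mean test has more power. Counts by arm go in the main report, so a reader can work out a crude difference. This is a secondary outcome, neither document controls multiplicity across secondary outcomes, and no trial decision rests on it.

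Much of that stands, and it supports keeping the mean model. It does not account for dropping the comparison. The only alternative that protocol 12.2.4 names is time-to-event analysis, which would still use reaching continence as the event, and the SAP gives no reason for replacing the proportion. The Kaplan-Meier curve is no substitute: it is untested, and section 4.9.3 as worded censors men on reaching ICIQ 5 or less, which is the event. SAP 2.1 allows further justified analyses, but one added later would not be pre-specified.

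A reader might infer that the trial has lost power for continence. The documents do not support that: working step 4 goes in either direction, on assumptions the documents cannot settle. A reader might also infer that the 89% is wrong or that the SAP misuses it. Neither is shown. The figure is attainable for the proportion, and the SAP makes no power claim for ICIQ.

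**Conclusion.** The point holds as a change of question. Secondary outcome #1 in the protocol is a between-arm comparison of proportions. In the SAP that proportion is described but not compared: no difference, interval or test is specified, overall or in non-BNSR men. The protocol's 89% belongs to the proportion and has no corresponding planned inference.

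It would go too far to say that continence is left unreported, since counts and a curve are planned, or that the mean analysis is inferior. What is missing is one estimate with its uncertainty, with an expected 95% half-width of about 8 to 10 points. That figure rests on 182 evaluable men per arm, a true 15-point difference, and assumed control rates of 15% to 70%. The improvement is worth making because it is cheap and lets the trial answer its own stated question; it does not threaten the primary result.

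**What to change.** In SAP 4.8, keep the linear model for the ICIQ score and add:

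- the difference between arms in the proportion with ICIQ 5 or less at 3 months, with 95% CI and p-value;
- the same at 6 months, as the protocol's sensitivity analysis;
- the 3-month comparison in non-BNSR men, under section 4.10.3.

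Either the protocol's unadjusted comparison of proportions or a logistic model with site, age and baseline ICIQ, standardised to a risk difference, would serve; name one in advance. State which of the mean and the proportion is the main continence result, say that the protocol's 89% power refers to the proportion, and give the reason for analysing the score as well.

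The cost is a short SAP edit and a few lines of code on a variable that section 3.6.3 already derives. The downside is one or two more secondary estimates without multiplicity control; the informal count of comparisons in section 4.1.3 should be updated to include them.
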